8.4.2 Analysis of Primary Objective(s)

8.4.2.1 Analysis of Primary Safety Objective(s)

8.4.2.1.1 Analysis of Extent of Exposure

The number of subjects actually receiving the first and second vaccination will be summarized by vaccine group.

8.4.2.1.2 Analysis of Solicited Local, Systemic and Other Adverse Events

Frequencies and percentages of subjects experiencing each AE occurring after first study vaccination, will be presented for each symptom overall and by maximum severity. Summary tables showing the occurrence of any local or systemic AE overall and at each time point will also be presented.

Post-vaccination solicited AEs reported from Day 1 to Day 7 will be summarized for the intervals Day 1-3, Day 4-7, Day 1-7 by maximal severity and by vaccine group, excluding the 30 minute measurement, which will be summarized separately.

The severity of solicited local AEs including injection-site erythema, injection-site induration, injection-site ecchymosis, and either injection-site tenderness (for children

ages 6 months through <3 year) or injection-site pain (for children 3 years and older). Injection-site erythema, induration and ecchymosis will be summarized according to categories: 1 to 10 mm, 11 to 25 mm, 26 to 50 mm, >50 mm. Injection site pain/tenderness and systemic AEs (except fever) occurring up to 7 days after each vaccination will be summarized according to “mild”, “moderate” or “severe”.

Body temperature will be summarized by 0.5 °C and 1.0 °C increments from 36.0°C up to $\geq 40^{\circ}\text{C}$ and will be broken down according by route of measurement. Fever, ie, body temperature $\geq 38^{\circ}\text{C}$ will also be categorized as mild (38.0-38.4°C), moderate (38.5-38.9°C), severe (39.0-40.0°C), and potentially life threatening ($\geq 40.0^{\circ}\text{C}$).

Each solicited local and systemic AE will also be further summarized as “none” versus “any”.

Implausible measurements (for further definition see the SAP) will be left out of the analysis.

Use of antipyretics and analgesics will be summarized by frequency: by type of use (prophylactic versus treatment) and percentage of subjects reporting use.

8.4.2.1.3 Analysis of Unsolicited Adverse Events

This analysis applies to all AEs occurring during the study, judged either as probably related, possibly related, or not related to vaccination by the investigator, recorded in AE eCRF, with a start date on or after the date of first vaccination. This analysis will include solicited AEs continuing beyond Day 7, which will be considered as possibly related AEs. AE starting prior to the first vaccination will only be listed. The original verbatim terms used by investigators to identify AEs in the eCRFs will be mapped to preferred terms using the Medical Dictionary for Regulatory Activities (MedDRA) dictionary. The AEs will then be grouped by MedDRA preferred terms into frequency tables according to system organ class.

All reported AEs, as well as AEs judged by the investigator as at least possibly related to study vaccine, will be summarized according to system organ class and preferred term within system organ class. These summaries will be presented by vaccination group. When an adverse event occurs more than once for a subject, the maximal severity and strongest relationship to the vaccine group will be counted.

Separate summaries will be produced for the following categories:

- SAEs
- AEs that are possibly or probably related to vaccine

- AEs of special interest
- New onset of chronic disease
- AEs leading to withdrawal from the study or the second vaccination

Data listings of all AEs will be provided by subject. In addition, AEs in the categories above will be provided as listed data.

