7.1.1 Solicited Adverse Events

The term “reactogenicity” refers to solicited signs and symptoms (“solicited adverse events”) occurring in the hours and days following a vaccination, to be collected by the subject’s parent(s)/LAR(s)/caregiver for 7 consecutive days, using a pre-defined Subject Diary Card. In this study there will be 2 versions of the Subject Diary Card; one version for children <3 years and one version for children ages 3 years and older.

The following solicited adverse events are included in the Subject Diary Card. Each adverse event is to be assessed according to defined severity grading scales.

For children ages 6 months through <3 years, solicited local AEs will include injection-site erythema, injection-site induration, injection-site ecchymosis, and injection-site tenderness; solicited systemic AEs will include change in eating habits, shivering, sleepiness, irritability, vomiting, diarrhea, and body temperature $\geq 38.0^{\circ}\text{C}$.

For children ages 3 years and older, solicited local AEs will include injection-site erythema, injection-site induration, injection-site ecchymosis, and injection-site pain; solicited systemic AEs will include loss of appetite, nausea, fatigue, malaise, generalized myalgia, generalized arthralgia, headache, shivering/chills, vomiting, diarrhea, and body temperature $\geq 38.0^{\circ}\text{C}$.

Solicited local or systemic adverse event continuing beyond Day 7 after vaccination, must also be recorded as an unsolicited AE on the AE eCRF.

Other Indicators of Reactogenicity

The use of analgesics/antipyretics will be captured as “absent” or “present” and will also be summarized by “for treatment” or “for prophylaxis”.

Instructions for Temperature Collection

Temperature should preferably be measured using the thermometer provided to the parent(s)/LAR(s) by the site staff. Ideally the subject’s temperature should be taken orally, however if for some reason it cannot be taken in this way, the alternate route of administration should be recorded on the Subject Diary Card.

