7.1.3 Evaluation of Adverse Events

Every effort should be made by the investigator to evaluate safety information reported by a subject for an underlying diagnosis and to capture this diagnosis as the event on the AE page. In other words, the practice of reporting only symptoms (eg, "cough" or "ear pain") are better reported according to the underlying cause (eg, "asthma exacerbation" or "otitis media").

The severity of events reported on the adverse events eCRF will be determined by the investigator as:

Mild: transient with no limitation in normal daily activity.

Moderate: some limitation in normal daily activity.

Severe: unable to perform normal daily activity.

The relationship of the study treatment to an AE will be determined by the investigator based on the following definitions:

1. Not Related

The AE is not related to an investigational vaccine if there is evidence that clearly indicates an alternative explanation. If the subject has not received the vaccine, the timing of the exposure to the vaccine and the onset of the AE are not reasonably related in time, or other facts, evidence or arguments exist that reasonably suggest an alternative explanation, then the AE is not related.

2. Possibly Related

The administration of the investigational vaccine and AE are considered reasonably related in time and the AE could be explained by exposure to the investigational vaccine or by other causes.

3. Probably Related

Exposure to the investigational vaccine and AE are reasonably related in time and no alternative explanation has been identified.

The relationship of the study treatment to an unsolicited AE will be determined by the investigator.

Note: all solicited AEs from Day 1 to Day 7 will be considered Adverse Drug Reactions (ADRs). Grading for severity of solicited local and systemic AEs is described in [section 7.1.1, Solicited Adverse Events](#).

Adverse events will also be evaluated by the investigator for the co-existence of any of the other following conditions:

- “New Onset of Chronic Disease”: an AE that represents a new diagnosis of a chronic medical condition that was not present or suspected in a subject prior to study enrolment.
- Adverse events leading to withdrawal: AEs leading to study or vaccine withdrawal.

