- **Pre-vaccination (will be mapped to MH):** start date before the date of first injection of study vaccine or indicated as on injection day but before injection.
- **Emergence during vaccination phase:** all other cases.

Note: If an AE start date is missing or unknown and no indication is provided on the timing, the AE will be considered as emergent.

When start and/or end dates of an AE are only partially known, AEs will be categorized as emergent before, during, or after vaccination phase using the following rules:

- If the partial end date is before ($<$) the first vaccination (i.e., year or year & month is/are before the study vaccination year or year & month) then the AE is pre-vaccination.
- If the partial start date is equal or after (\geq) the first study vaccination (i.e., year or year & month is/are after or the same as the first study injection year or year & month) then the AE is emergent during vaccination phase.

Statistical Analysis Plan, Protocol Number V87_30

06 MAY 2022 Final Version 1.0

All AEs emergent during vaccination phase will categorized as occurring during the period of 21 days following the last vaccination based on the start date. If start date is missing or incomplete, events will be counted as yes during the period of 21 days following the last vaccination.

Adverse events that meet none of the following criteria SAE, AESI, NOCD, or AE leading to withdrawal, and had a start date more than 21 days after the last vaccination are not to be recorded. However, if recorded, these AEs should be flagged (**i.e. exclusion flag**), excluded from analysis and listed separately.

The **maximum event severity** is the greatest severity associated with a preferred term (PT) for a reported AE according to the following order: Mild < Moderate < Severe.

Vaccination-related Adverse Events are those for which the cause has been evaluated by the investigator, and recorded as possibly related, probably related or unknown/ missing.

Prior and Concomitant Medications

All medications will be characterized according to the start and end date of occurrence related to the vaccination as follows:

- **Pre-vaccination:** start date before the date of first injection of study vaccine.
- **Concomitant:** start date before vaccination but continued after vaccination or start date after vaccination. The period Day 1- 43 (i.e. 21 days after the last study vaccination) will be labeled if the start date is on or before Day 43.

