13.3 Unsolicited Adverse Events

This analysis applies to all ongoing solicited AEs beyond seven days after the vaccination, all unsolicited AE's occurring during the study, judged either as probably related, possibly related, or not related to vaccination by the investigator, recorded in the AE eCRF, with a start date on (but with onset after vaccination) or after the date of vaccination. AE starting prior to study vaccination will only be listed.

The original verbatim terms used by investigators to identify AEs in the eCRFs will be mapped to PTs using the MedDRA dictionary.

The AEs will then be grouped by MedDRA PTs into frequency tables according to SOC. All reported AEs, as well as AEs judged by the investigator as at least possibly related to study vaccine, will be summarized according to SOC and the PT within SOC. These summaries will be presented by the vaccination group. When an AE occurs more than once for a subject, the maximal severity and strongest relationship to the vaccine group will be counted.

The assignment to time intervals will be done by day of onset and not by days ongoing/persisting.

Statistical Analysis Plan, Protocol Number V87_30

06 MAY 2022 Final Version 1.0

The summaries will be presented by SOC and PT and different periods of onset depending on the category of events.

- From Day 1 to 21 days after the last vaccination:

- AE
- AE by maximum severity
- Related (i.e. at least possible) AE
- SAEs
- Related SAEs
- AESIs
- NOCD
- AEs leading to withdrawal (from the study or the second vaccination)
- Deaths.

- From Day 1 to end of study:

- SAEs
- Related SAEs
- AESIs
- NOCD
- AEs leading to withdrawal (from the study or the second vaccination)
- Deaths.

A summary of subjects with solicited and unsolicited non-serious treatment emergent adverse events reported by >5% of subjects sorted by system organ class and preferred term will be provided for clinicaltrials.gov and EudraCT.eu posting purposes.

Data listings of all AEs will be provided by the subject. In addition, AEs in the categories above will be provided as listed data.

Statistical Analysis Plan, Protocol Number V87_30

06 MAY 2022 Final Version 1.0

All tables will be produced overall and by age subgroup. The overview summary as well as the summary of AEs and SAEs will be also be presented by the other subgroups.

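### The SAP omits the protocol's rule that solicited AEs continuing beyond Day 7 count as possibly related, so any such event recorded 'not related' would be left out of the related-AE table

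*Protocol*

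**What the plan says.** **Protocol.** Section 7.1.1 says a solicited AE that continues past Day 7 after vaccination "must also be recorded as an unsolicited AE on the AE eCRF". Section 7.1.3 treats the first week by convention, "all solicited AEs from Day 1 to Day 7 will be considered Adverse Drug Reactions", and for unsolicited events says: "The relationship of the study treatment to an unsolicited AE will be determined by the investigator". 'Not related' is one of the three categories available. Section 8.4.2.1.3 then sets an analysis rule for the persisting events: "This analysis will include solicited AEs continuing beyond Day 7, which will be considered as possibly related AEs". The next paragraph of that section describes the related summary as covering AEs "as well as AEs judged by the investigator as at least possibly related to study vaccine". The section also asks for a separate summary of AEs possibly or probably related to vaccine.

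**SAP.** Section 13.3 opens with "This analysis applies to all ongoing solicited AEs beyond seven days after the vaccination" and continues much as the protocol does, but without the sentence on relatedness. It lists a table of related AEs (at least possible) and, separately, a table of related SAEs. Section 8.7 says vaccination-related AEs "are those for which the cause has been evaluated by the investigator, and recorded as possibly related, probably related or unknown/ missing". It has no separate provision for persisting solicited AEs. Section 16, on changes to the planned analysis, reads as not applicable.

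**The concern.** A programmer working from the SAP would read relatedness from the AE eCRF field and would have no instruction to apply the protocol's rule. The related-AE table could then omit events that the protocol says to treat as possibly related, and nothing in the SAP would tell the reader that the rule had been dropped.

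Events that can persist include diarrhea, vomiting and fever in young children, where an investigator may well find another explanation and record 'not related'. The same reaction would then be an adverse drug reaction by convention through Day 7 and sit outside the related table once it was entered on the AE page as an unsolicited event.

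What is at stake is agreement between the reported related-AE counts and the protocol, in a trial with safety among its primary objectives. No primary safety endpoint is itself defined by relatedness.

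**Working it through.** There is no stated figure to reproduce. The check compares the two rules case by case, followed by an illustration under assumed rates.

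**Step 1: the two rules applied to one solicited AE that continues beyond Day 7.**

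| Relationship on the AE eCRF | Protocol 8.4.2.1.3, persistence clause | SAP 8.7 definition |
|---|---|---|
| Probably related | related | related |
| Possibly related | related | related |
| Unknown or missing | related | related |
| Not related | related | not related |

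The rules part only in the last row, and there the SAP gives the lower count. For this group of events the SAP count is therefore less than or equal to the protocol count.

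**Step 2: can the last row occur?** Yes. Protocol 7.1.1 sends the event to the AE eCRF as unsolicited, and Protocol 7.1.3 has the investigator assign its relationship with 'not related' available.

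**Step 3: when does a subject actually leave a row of the table?** Both documents count the strongest relationship when an AE recurs within a subject. A subject drops out of a row only if the persisting event is recorded 'not related' and no other related AE places that subject in the same row.

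**Step 4: illustration of size.** Let N be the number of subjects, p the share with a solicited AE persisting beyond Day 7, and q the share of those recorded 'not related' and not otherwise in the row. Expected subjects lost = N × p × q. The chance of at least one among 420 = 1 − (1 − p × q)^420. N comes from Protocol Table 6.1 (about 70 per arm) and section 8.5 (420 in total). The documents give neither p nor q. Both are assumptions: p from 2% to 10%, q from 0 to 50%.

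| p | q | p × q | Expected per arm of 70 | Expected of 420 | Chance of at least one in 420 |
|---|---|---|---|---|---|
| any | 0 | 0 | 0 | 0 | 0 |
| 2% | 10% | 0.2% | 0.14 | 0.84 | 57% |
| 5% | 25% | 1.25% | 0.88 | 5.25 | above 99% |
| 10% | 50% | 5% | 3.5 | 21 | above 99% |

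Second row worked: 420 × 0.02 × 0.10 = 0.84, and 1 − 0.998^420 = 0.57. Across the assumed range the shift is 0 to 5 percentage points of an arm.

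**The case against.** **The protocol is not explicit about an override.** It does not say that the persistence clause prevails over a recorded 'not related', and its next paragraph describes the related summary as investigator-judged, wording the SAP follows closely. This stands in part. Treating the events as possibly related is the natural reading of the clause, which would otherwise do nothing, but the ambiguity begins in the protocol and has to be settled there too.

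**The change of status after Day 7 is not the SAP's creation.** This stands. The Day 1 to 7 convention and the investigator's role both come from Protocol 7.1.1 and 7.1.3. The SAP's part is to omit the clause that would have bridged them.

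**Persistence remains visible.** This stands. SAP 13.2 tabulates the number of days of each solicited AE, including time after Day 7, and the solicited AEs ongoing at Day 7. The all-AE and maximum-severity tables in 13.3 include these events whatever their causality. None of this corrects the related-AE table.

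**Stronger readings that a reader might infer and the documents do not support:**
- *The SAP relies on the investigator's judgement alone.* It does not: unknown or missing relationship also counts as related.
- *The related table will under-count.* That is conditional on at least one event meeting Step 3. Protocol 7.1.3 ties 'not related' to evidence or timing pointing elsewhere, which may be uncommon for a continuing injection-site reaction.
- *The whole table moves downward.* The SAP's unknown/missing rule, absent from Protocol 8.4.2.1.3, can add other AEs, so the net direction of the whole table is not fixed.
- *The comparison of formulations is distorted.* Assessments are made by blinded staff and the documents give no rates of persistence by arm. An unequal effect is possible if persistence differs by formulation, but nothing in the documents shows it.

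**Conclusion.** The omission is real: a protocol classification rule is absent from the SAP sections that should carry it out, and SAP 16 does not declare a departure. Any persisting solicited AE recorded 'not related' would be left out of the SAP's related-AE table although the protocol's clause counts it. For these events the SAP count can be equal or lower, never higher.

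The amount cannot be estimated from the documents. The range of 0 to 5 percentage points rests wholly on assumed values of p and q, and includes no effect at all. The conclusion also assumes that the protocol clause is meant to govern classification in the related summary.

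This is a minor alignment point. It affects a supporting descriptive table, no primary endpoint and no hypothesis test, but it is specific and cheap to settle.

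**What to change.** Preferred, as an SAP amendment before unblinding:

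1. In SAP 8.7, define a flag for solicited AEs continuing beyond Day 7 after a vaccination. State that flagged events are set to at least possibly related in the related-AE summary, and that this applies even where 'not related' was recorded.
2. In SAP 13.3, restore the protocol's clause by reference to the flag. Keep the investigator's recorded assessment in the listings, and show the related-AE table both with and without the rule.
3. Leave the Related SAEs table on the investigator's assessment. Protocol 7.1.4 gives the investigator the causality decision for SAEs, and a solicited AE can meet the SAE definition, so a rule for every related-event table would reach too far.
4. Reconcile Protocol 8.4.2.1.3, so that the investigator-judged wording of the related summary and the persistence clause agree.

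Alternatively, if the sponsor prefers the recorded assessment throughout, declare and justify that departure in SAP 16.

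The SAP cost is one or two sentences, one derived flag and one repeated table. The protocol needs a wording clarification. No new data are collected.

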8.4.2.1.4 Analysis of Safety Laboratory Values

Not applicable for this study.

8.4.2.2 Analysis of Primary Efficacy Objective(s)

Not applicable for this study.

8.4.2.2.1 Statistical Hypotheses

This study does not have statistical hypotheses.

8.4.2.2.2 Analysis Sets

All immunogenicity analyses (primary, secondary, and exploratory) will be performed on the PPS Immunogenicity. The primary immunogenicity analyses will be also performed based on the FAS Immunogenicity if the percentage of subjects excluded from the PPS immunogenicity is greater than 5%. All solicited safety analyses will be performed in solicited safety set. All unsolicited safety analyses will be performed on the unsolicited safety set. Further details are given in [Section 8.3, Analysis Sets](#).

8.4.2.2.3 Statistical Methods

8.4.2.3 Analysis of Primary Immunogenicity Objective(s)

The antibody titers below lower limit of detection (LLD) will be coded as half of LLD (for example, 5 if LLD is 10). Missing immunogenicity data will be excluded from analysis of immunogenicity endpoints. Imputation methods will therefore not be applied. Sensitivity analyses may be considered to assess the impact of missing data in case of substantial missing data.

For analysis requiring quantitative summarization of antibody titers (such as GMT or GMR) all antibody titers will be \log_{10} -transformed. Geometric mean ratios with 95% CIs will be calculated by estimating arithmetic means and 95% CIs for a normal variate on

log₁₀-transformed scale, then back-transformation of these statistics using exponentiation at the base of 10.

For analysis of binary data (ie, percentage of subjects with seroconversion and percentage of subjects with titer $\geq 1:40$), the counts and percentages will be determined, the CIs will be calculated using Clopper-Pearson method.

Seroconversion will be defined as either of the two conditions: subjects with a baseline titer $< 1:10$ by either HI or MN assay with a post-vaccination titer $\geq 1:40$ OR subjects with baseline titer $\geq 1:10$ by either HI or MN assay with a 4-fold or higher increase in post-vaccination titer.

No formal statistical hypothesis will be tested.

8.4.2.3.1 Statistical Hypotheses

This study does not have statistical hypotheses.

